8.2 Randomisation Procedures

All enrolled participants will be entered onto an enrolment log.

Participant randomisation will be undertaken remotely at site using Sealed Envelope, an online service for the randomisation of participants in a clinical trial.

Following participant consent, and confirmation of eligibility (see section 8.1 for pre-treatment assessments) the randomisation procedure described below will be carried out.

Participants will be randomised to receive the trial drug added to their treatment or to continue to receive existing treatment alone. The investigator will enter the patient's initials, gender, date of birth, date of consent, criteria fulfilment and MSA phenotype strata into the Sealed Envelope secure website. A random sequence for study arm allocation will be computer generated by a randomisation service provider (Sealed Envelope.com). Sealed Envelope will provide a unique trial identification code for each recruited participant. Blocking will be used within strata to enable achievement of approximately equal numbers in each group.

Strata 1= Phenotype consistent with MSA-C.

Strata 2= Phenotype consistent with MSA-P

A list of the trial identification codes and treatment allocation will be stored in a secure cabinet with the study team. The randomisation list will be sufficiently long to enable continued randomisation should any patients drop out within the first 9 months. All randomisation procedures will take place during working hours.

Participants are considered to be enrolled into the trial following: consent, pre-treatment assessments (see section 8.1), confirmation of eligibility, completion of the randomisation process, allocation of the participant trial number and treatment by the remote system.

8.3 Treatment Schedule

For participants randomised to receive the trial drug they will receive 2mg Exenatide once-weekly for 48 weeks via subcutaneous injection. Astra-Zeneca announced that they will discontinue manufacturing of Bydureon from March 2021 and that this would be replaced by

the Bydureon BCise. There is no difference to the dose of exenatide contained between the devices. Patients who have already started on Bydureon will be reconsented and given new instructions about how to use the updated device.

The first dose will be administered in clinic following injection teaching and the patient will be given sufficient number of pens to continue injections until their 12 week follow up visit. Each participant will be shown an online video instruction specifically for the Bydureon or Bydureon BCise pen injections, which they can revisit as necessary. Each subsequent injection will be given every 7 days at home by self-administration. Injections will be given into the abdomen, arm, thigh or buttocks. Participants will be given a dosing diary to record the time and day of all injections administered.

The control group of patients are very important in view of the continued but variable rate of the neurodegenerative process of MSA.

Patients will continue to see their treating neurologist at normally scheduled appointments. Adjustment to MSA medications will be permitted based on the clinical judgement of the treating neurologist and/or the clinical trial team to optimise symptom control throughout the duration of the trial. Doses of all medications will be recorded at each trial visit.

8.3.1 *Dose Modifications*

Patients experiencing abdominal pain consistent with a clinical diagnosis of pancreatitis will receive investigation and treatment according to NHS standard of care and the trial medication will be stopped pending confirmation or exclusion of the diagnosis. Confirmation of a diagnosis of acute pancreatitis will result in the trial medication being permanently stopped.

Patients found to have an elevation in serum Amylase (>50% above baseline and >50% above the laboratory reference range) will have a clinical assessment and have the test repeated after 1 week. If the amylase remains elevated, a clinical decision will be made whether to temporarily withdraw exenatide until the amylase return to the normal range or permanently withdraw exenatide.

Patients developing clinical suspicion of thyroid malignancy will receive treatment according to NHS standard of care and the trial medication will be stopped.

Patients experiencing excessive/undesirable weight loss (>10% of body weight during a 12 week interval) or unacceptable adverse effects will have a clinical assessment and a decision regarding temporary withdrawal of study medication will be made.

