3.1 Assessment and management of risk

The table below summarises the risks, frequencies and mitigations of the IMP(s)

Name of IMP(s) / NIMP	Potential risk	Risk Frequency	Risk Management
Exenatide	Weight loss	Common	Underweight people will not be recruited. Patients losing weight too rapidly (>10% body weight per month) will temporarily stop the IMP.
Exenatide	Nausea/ Vomiting	Very common	In most cases, nausea is mild and self limiting. In more severe cases, patients will be prescribed a temporary course of Domperidone.
Exenatide	Diarrhoea	Very common	In most cases, diarrhoea is mild and self limiting. Symptomatic and supportive treatment will be given as necessary.
Exenatide	Decreased Appetite	Common	In most cases, loss of appetite is transient and self limiting. Weight will be measured and exenatide will be transiently stopped if weight loss exceeds 10% of body weight per month.
Exenatide	Headache	Common	In most cases, headache is transient and self limiting. Participants will be assessed and given standard of care treatment for persistent headaches.
Exenatide	Dizziness	Common	In most cases, dizziness, is transient and self limiting. Participants will be assessed and given standard of care treatment for persistent dizziness.

Short title: Exenatide once-weekly as a treatment for Multiple System Atrophy Sponsor code: 125591

Exenatide	Dyspepsia/ Abdominal pain	Common	In most cases, abdominal pain is transient and self limiting. Any suspicion of pancreatitis will lead to temporary discontinuation of exenatide until pancreatitis has been excluded. Participants will be assessed and given standard of care treatment for persistent abdominal pain.
Exenatide	Abdominal Distension/ Flatulence	Common	In most cases, abdominal distension/flatulence is transient and self limiting. Participants will be assessed and given standard of care treatment for persistent abdominal distension/flatulence.
Exenatide	Constipation	Common	In most cases, constipation is transient and self limiting. Participants will be assessed and given standard of care treatment for persistent constipation.
Exenatide	Anaphylactic reaction	Rare	Patients will self administer their first Exenatide injection in the trial centre under supervision by the trial team.

The table below summarise the risks and mitigations of all test above standard care that are being performed in a table:

Intervention	Potential risk	Risk Management

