Unexpected	An adverse event which is not consistent with the information about the IMP listed in current approved Reference Safety Information (RSI) for the trial.

The RSI to be used to assess expectedness against the IMP is:

SmPC for Bydureon (exenatide) 2 mg for prolonged-release suspension for injection in pre-filled pen (BCise) (AstraZeneca UK Limited).

The following events listed below describe expected procedural/disease related AEs: The most frequent adverse reactions were mainly gastrointestinal related (nausea which was the most frequent reaction and associated with the initiation of treatment and decreased over time, and diarrhoea). In addition, injection site reactions (pruritus, nodules, erythema), hypoglycaemia (with a sulphonylurea), and headache occurred. Most adverse reactions associated with prolonged-release exenatide were mild to moderate in intensity.

9.3.4 *Seriousness*

All events are assessed for seriousness as defined for an SAE in section 9.1. Specific adverse events that require expedited reporting as SAEs are detailed in section 9.3.5.

9.3.5 *Other Notifiable Adverse Events*

Suspicion of chronic pancreatitis based on a rise in serum amylase greater than 50% above both baseline level AND the laboratory reference range will be notified in an expedited manner in the same way as an SAE.

Overdose and potential drug induced liver injury (DILI) events must be handled as SAEs (see section 9.8).

All safety events as described above will be treated as SAEs and reported in line with the procedures set-out in section 9.4 apart from regulatory reporting.

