9.4 Procedures for recording and reporting Serious Adverse Events

All serious adverse events (SAEs/SARs/SUSARs) will be recorded in the medical records and the CRF, and the sponsor's SAE Recording Log. The SAE Recording Log of SAEs will be reported to the sponsor at least once or twice per year.

All SAEs will be recorded from baseline visit until 10 weeks after completion of IMP (phone call at 58 weeks). From the 58 week phone call and the 96 week visit only SAEs related to IMP or other trial intervention need to be recorded in the CRF.

All SAEs must be recorded on a Serious Adverse Event (SAE) Reporting Form. The CI/PI or designated individual will complete the sponsor's SAE Reporting Form and the form will be

Short title: Exenatide once-weekly as a treatment for Multiple System Atrophy Sponsor code: 125591

emailed to the Sponsor [contact] and within 24 h of his / her becoming aware of the event. The Chief or Principal Investigator will respond to any SAE queries raised by the sponsor as soon as possible.

Completed SAE forms must be sent within 24 hours of becoming aware of the event to the Sponsor
Email forms to [contact]

[figure not shown]
Reporting to the sponsor will be completed as per the sponsor's SOP and using the UCL SAE Reporting Form (INV/S05) as amended for the trial.

SAEs will be reported to the sponsor until the end of the trial. SAR and SUSAR will need to be reported to the Sponsor irrespective of how long after IMP administration the reaction has occurred.

Participants must be followed up until clinical recovery is complete and laboratory results have returned to normal or baseline values, or until the event has stabilised. Follow-up should continue after completion of protocol treatment and/or trial follow-up if necessary.

Follow-up SAE forms (clearly marked as follow-up) should be completed and emailed to the JRO as further information becomes available.

Flow Chart for SAE reporting

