11.2 Sample size and recruitment

11.2.1 Sample size calculation

The recent rasagiline for MSA (MSA-Ras) trial evaluated rasagiline versus placebo using the UMSARS total (Parts I and II) as the primary efficacy measure after 48 weeks treatment. Patients in the placebo group declined by mean 7.8 points (SD 10.4 – Werner et al. 2015).

Therefore, on the basis of this previously collected data and with a two-sided 5% significance level, we estimated that a sample size of 40 patients (20 per group) would be required to detect a difference of 5 total UMSARS points between the two groups, assuming a correlation between baseline and final disease severity of 0.85. These calculations were based on a common SD of 10.4, 80% power and an overall type 1 error rate of 5%. A 5 point difference between groups would be a clinically important effect size. Based on a 20% dropout rate as reported from previous trials, the sample size would be 50 (25 per arm).

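### For an amylase rise that the protocol itself calls suspected pancreatitis, the dosing rule in section 8.3.1 does not match the stop-until-excluded rule in section 3.1

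*Protocol*

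**What the plan says.** Three parts of the protocol bear on suspected pancreatitis.

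- **Section 3.1, risk table, dyspepsia/abdominal pain row:** "Any suspicion of pancreatitis will lead to temporary discontinuation of exenatide until pancreatitis has been excluded".
- **Section 8.3.1, Dose Modifications:** there are two paths. For abdominal pain that fits pancreatitis, "the trial medication will be stopped pending confirmation or exclusion of the diagnosis", and then "Confirmation of a diagnosis of acute pancreatitis will result in the trial medication being permanently stopped". For a raised amylase, the participant is assessed clinically and retested after one week. If the value is still high, "a clinical decision will be made whether to temporarily withdraw exenatide until the amylase return to the normal range or permanently withdraw exenatide".
- **Section 9.3.5, Other Notifiable Adverse Events:** the event to be notified urgently is "Suspicion of chronic pancreatitis based on a rise in serum amylase greater than 50% above both baseline level AND the laboratory reference range". It is handled as a serious adverse event for notification, apart from regulatory reporting. No dosing instruction is attached.

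The SAP does not address dosing rules.

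**The concern.** Section 9.3.5 gives the amylase rise a diagnostic label, and section 3.1 ties that label to a dosing consequence: stop, and stay stopped until the diagnosis is ruled out. Section 8.3.1 is where staff will look when deciding whether to give the next injection. For the same rise it gives a different instruction and refers to neither of the other sections.

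At stake is the handling of a participant with a raised amylase and no abdominal pain. Staff working from 3.1 would stop the drug at once and keep it stopped until pancreatitis was excluded. Staff working from 8.3.1 could leave it running until the repeat test, withdraw it temporarily, and restart when amylase was normal, with no record that the diagnosis had been considered and excluded. Injections are self-administered at home, and 12 pens are dispensed at a time from week 12. The participant may therefore already hold supplies, and the written instruction matters.

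**Working it through.** No sample size, power or event count bears on this point. The check is whether the triggers are the same, and then whether the actions are.

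**Step 1: the triggers.** Let A be the amylase value, B the baseline value and U the upper limit of the reference range (reading the reference range as its upper limit is an assumption). More than 50% above means more than 1 + 0.50 = 1.5 times.

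- Section 8.3.1 amylase path: A > 1.5 × B and A > 1.5 × U.
- Section 9.3.5: A > 1.5 × B and A > 1.5 × U.

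These are identical. Every rise that enters the 8.3.1 amylase path is, on the same result, a suspected chronic pancreatitis under 9.3.5. Section 9.3.5 does not wait for a repeat test.

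**Step 2: the actions.**

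| Rule | Drug at first trigger | What ends a temporary stop | Mandatory permanent stop |
|---|---|---|---|
| 3.1, abdominal-pain row | Stopped | Pancreatitis excluded | None stated |
| 8.3.1, pain path | Stopped | Diagnosis excluded | Confirmed acute pancreatitis |
| 8.3.1, amylase path | No hold stated; retest after 1 week | Amylase normal | None; permanent withdrawal is a clinical decision |
| 9.3.5 | No dosing instruction | Not addressed | Not addressed |

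**Step 3: the differences.** The 8.3.1 amylase path departs from 3.1, read with 9.3.5, on two points.

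1. *Start of the stop.* Under 3.1 it begins at suspicion. Under 8.3.1 it begins, if at all, after the repeat test. With an injection every 7 days and a retest after 1 week, about one dose falls in that interval.
2. *End of the stop.* Under 3.1 it ends when the diagnosis is excluded. Under 8.3.1 it ends on a laboratory value. The neighbouring pain path shows that the protocol treats these as different endpoints.

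There is also a gap in the permanent stop. It is written for acute pancreatitis, whereas the condition that 9.3.5 suspects at this threshold is chronic. Section 7.3 excludes anyone with a history of pancreatitis and makes no such distinction.

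**Step 4: does another section supply the restart condition?** Section 9.4 follows an event until the participant has recovered and "laboratory results have returned to normal or baseline values, or until the event has stabilised". That governs follow-up of the event, not dosing. Sections 8.8 and 8.10 permit discontinuation on judgement. None of these says when exenatide may be resumed.

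**The case against.** The strongest reply is that the protocol already contains the rule. Section 9.3.5 makes the rise a suspicion, 3.1 says that any suspicion stops drug until exclusion, and the conditions in 3.1 and 8.3.1 can be read as cumulative: normal amylase and exclusion. On that reading, a restart on normal amylase alone would depart from the protocol even though it satisfies 8.3.1. A reader might infer from 8.3.1 that the protocol has no exclusion rule, or that it knowingly allows re-dosing in suspected pancreatitis. The documents do not support either inference, because 3.1 and 9.3.5 together say otherwise.

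There are also real safeguards. The amylase path requires a clinical assessment and a clinical decision, and permanent withdrawal is one of the options. Section 8.8 allows treatment to stop for unacceptable toxicity. Section 8.10 lists an unacceptable adverse event as an individual stopping rule, with the decision on continuation made by the Trial Management Group with sponsor input. Each qualifying rise goes to the sponsor within 24 hours (9.3.5 and 9.4), and that group reviews serious events (13.1). Handling a painless laboratory rise more gradually than suggestive pain is also a defensible clinical choice.

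Most of this stands, and it limits the severity. It does not remove the inconsistency. The 3.1 sentence sits in a row about dyspepsia and abdominal pain, where someone dealing with a painless rise may not look. Section 8.3.1 does not point to it and gives a different endpoint. The oversight provisions require notification and judgement but state no restart condition, and the management group meets every 3 months while dosing is weekly.

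**Conclusion.** The point holds as a minor internal inconsistency in a safety rule. For one and the same amylase rise, 3.1 with 9.3.5 gives stop-until-excluded. Section 8.3.1 gives no hold before the repeat test, a restart on normal amylase alone, and no mandatory permanent stop for chronic pancreatitis.

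A reader might also infer that a participant with confirmed chronic pancreatitis would be kept on drug. That goes too far: 8.8 and 8.10 allow the drug to be stopped. What is missing is the obligation.

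No count of affected participants can be given, because the documents state no rate of amylase rise or of pancreatitis. A tally of doses remaining after a restart would depend on assumed dates and would not measure harm. The rule can affect dosing only in the exenatide arm (about 25 participants), mainly through the scheduled amylase tests at weeks 12, 24 and 36. The primary analysis is unaffected in principle, since participants who stop treatment stay in follow-up (8.8) and are analysed as randomised (11.4.2).

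The conclusion assumes that the reference range means its upper limit in both sections, and that staff take dosing instructions from 8.3.1.

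**What to change.** Amend section 8.3.1 as follows.

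1. Hold exenatide at the first amylase result that meets the threshold, and tell the participant not to use pens already at home.
2. Allow restart only when amylase is back in the normal range and the investigator has documented that pancreatitis is excluded, using standard-of-care investigation as on the pain path.
3. Require a permanent stop for confirmed pancreatitis, acute or chronic, on either path.
4. Cross-refer 8.3.1 with the abdominal-pain row of 3.1 and with 9.3.5, so that all three give one rule.

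This is a few lines in the next amendment. The cost is an occasional work-up in a participant with a raised amylase, which 3.1 already implies, and a few missed doses while the drug is held, including some for rises that prove transient. No change to the SAP is needed.

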8.4 Subsequent assessments and procedures

Week 4 (+/-1 week) – telephone call

The study nurse will call the participants to ensure the participants are taking their medication according to the protocol requirements and completing their trial diary as required. They will also perform a concomitant medication and AE check.

Week 12 assessments – Visit 3

At 12 weeks after baseline evaluation, each patient will be telephoned 1 week prior to remind them of their visit

Participants will attend the research centre for the following trial procedures:

- Physical Examination (if deemed necessary by trial clinician for clinical purposes)
- Routine blood tests (FBC, U&E, LFT, glucose, amylase, HbA1c, PT and APTT)
- Serum collection
- Vital signs including weight
- UMSARS Part II (videotaped)
- UMSARS Part I, III and IV
- The Unified Dystonia Rating Scale
- MoCA
- Timed Motor tests
- BDI-II
- Concomitant Medications review
- Adverse Events review
- Dispensing of 12 exenatide (Bydureon or Bydureon BCise) pens (if randomised to receive exenatide).

All participants will be invited for face to face visits at all timepoints. If a participant is unable or unwilling to attend any of the follow up assessments (12,24,36,48,96 weeks), they may be offered the option of a home visit by one or more members of the trial clinical team if staffing levels permit. These participants will be asked to consent to home visits. Assessments will be performed as per protocol. Weight will be measured only if the participant is able to stand, and weighing scales are available. Dispensing of IMP will be performed by trial pharmacy and transported to the patient in an appropriate Cool Bag with temperature logger by the clinical trial team.

Week 24 assessments – Visit 4

At 24 weeks after baseline evaluation, each patient will be telephoned 1 week prior to remind them of their visit. They will be asked not to have eaten and to have drunk water only for 6 hours to enable fasting blood samples to be taken.

Participants will attend the research centre for the following trial procedures:

- Physical Examination (if deemed necessary by trial clinician for clinical purposes)
- Neurological Examination (if deemed necessary by trial clinician for clinical purposes)
- Fasting blood tests (FBC, U&E, LFT, glucose, amylase, insulin, c-peptide, HbA1c)
- Serum collection
- Vital signs including weight
- UMSARS Part II (videotaped)

Short title: Exenatide once-weekly as a treatment for Multiple System Atrophy Sponsor code: 125591

- UMSARS Part I, III and IV
- Timed motor tests
- COMPASS Select
- COMPASS Change
- The Unified Dystonia Rating scale
- BDI-II
- MoCA
- Concomitant Medications review
- Adverse Events review
- Dispensing of 12 exenatide pens (if randomised to receive exenatide).

Week 36 assessments – Visit 5

At 36 weeks after baseline evaluation, each patient will be telephoned 1 week prior to remind them of their visit.

Participants will attend the research centre for the following trial procedures:

- Physical Examination (if deemed necessary by trial clinician for clinical purposes)
- Routine blood tests (FBC, U&E, LFT, glucose, amylase and HbA1c)
- Serum collection
- Vital signs including weight
- UMSARS Part II (videotaped)
- UMSARS Part I, III and IV
- Timed motor tests
- The Unified Dystonia Rating scale
- BDI-II
- MoCA
- Concomitant Medications review
- Adverse Events review
- Dispensing of 12 exenatide (Bydureon or Bydureon BCise) pens (if randomised to receive exenatide).

Week 48 assessments – Visit 6

At 48 weeks after baseline evaluation, each patient will be telephoned 1 week prior to remind them of their visit. They will be asked not to have eaten and to have drunk water only for 6 hours to enable fasting blood samples to be taken.

Participants will attend the research centre for the following trial procedures:

- Physical Examination (if deemed necessary by trial clinician for clinical purposes)
- Neurological Examination (if deemed necessary by trial clinician for clinical purposes)

Short title: Exenatide once-weekly as a treatment for Multiple System Atrophy Sponsor code: 125591

- Fasting blood tests (glucose, insulin and c-peptide)
- Routine blood tests (FBC, U&E, LFT, glucose, amylase, HbA1c, PT and APTT)
- Serum collection
- Lumbar puncture for CSF collection
- Vital signs including weight
- UMSARS Part II (videotaped)
- UMSARS Part I, III and IV
- Timed motor tests
- COMPASS Select
- COMPASS Change
- MSA-QoL scale
- The Unified Dystonia Rating scale
- BDI-II
- MoCA
- Concomitant Medications review
- Adverse Events review
- Axivity lumbar sensor

If a patient cannot attend the clinical research facility and is being assessed via a home visit, no attempt will be made to perform a lumbar puncture and this missed assessment will be recorded as a protocol deviation.

Week 58 (+/-1 week) telephone call

The study nurse will call the participants to perform an adverse event check.

Week 96 assessments – Visit 7

At 96 weeks after baseline evaluation, each patient will be telephoned 1 week prior to remind them of their visit.

Participants will attend the research centre for the following trial procedures:

- Physical Examination (if deemed necessary by trial clinician for clinical purposes)
- Neurological Examination (if deemed necessary by trial clinician for clinical purposes)
- Serum collection
- Vital signs including weight
- UMSARS Part II (videotaped)
- UMSARS Part I, III and IV
- Timed motor tests
- COMPASS Select
- COMPASS Change
- MSA-QoL scale
- The Unified Dystonia Rating scale
- BDI-II
- MoCA

- Concomitant Medications review
- Adverse Events review

8.5 *Laboratory Assessments and Procedures*

Local laboratories

The following tests will be carried out at Local Laboratories:

- Routine bloods (FBC, U&E, LFT, glucose, amylase, HbA1c, PT and APTT)
- Fasting bloods (glucose, insulin, c-peptide, triglycerides, amylase, FBC, U&E, LFT and HbA1c)
- Urine pregnancy test

These are all standard hospital laboratory tests and will be performed according to standard treatment processes.

Research Samples

Serum samples will be processed, aliquoted and frozen in accordance with laboratory manual. Patients may consent to their samples being kept for future research. Future analyses will be planned as appropriate in accordance with clinical results, future funding application and latest knowledge.

8.6 *Clinical Procedures and Data Collection*

- Medical history: review of past medical history, family history, previous imaging, previous genetics tests and MSA medication history.
- Physical examination: The following sites will be examined: chest, heart, abdomen, skin, and lymph nodes; and the following systems will be assessed: musculoskeletal and neurological.
- Neurological examination: The following will be examined: mental status, level of consciousness, sensory function, motor function, cranial nerve function and reflexes.
- Electrocardiogram: A standard 12-lead electrocardiogram will be performed.
- Vital signs: For vital signs measurement the participant's position and arm used for the measurement will be noted. Vital signs include systolic and diastolic blood pressure, respiratory rate, oxygen saturation, weight, temperature and pulse rate.
- Concomitant Medication: All over-the-counter or prescription medication, vitamins, and/or herbal supplements will be recorded.

- The Montreal Cognitive Assessment is a 30-point test that assesses several cognitive domains to detect cognitive impairment.
- The Beck's Depression Inventory-II is a patient rated depression severity scale.
- The Unified MSA Rating Scale (UMSARS) is a multidimensional, reliable, and valid scale for semi quantitative assessment of MSA patients with high internal consistency and substantial-to-excellent interrater agreement and is sensitive to change. It focuses on all aspects of the disorder, including autonomic, cerebellar, and parkinsonism manifestations. USMARS has an Activities of Daily Living score (UMSARS Part 1, 12 questions); a Motor Examination score (UMSARS Part 2, 14 questions); Autonomic examination score (UMSARS Part 3) and a global disability scale (UMSARS Part 4). Part 2 will be videotaped to ensure there is the option to retrospectively score the participants by blinded raters if there are concerns regarding bias in view of this being an open label trial. All videos will be stored in an appropriate secure encrypted storage facility which can only be accessed by members of the research team.
- The Composite Autonomic Symptom (COMPASS) Select is a subset of the full COMPASS consisting of 46 questions in 5 domains (orthostatic intolerance, secretomotor, bladder, constipation, and sleep), leading to a total score between 0 and 125, with a higher score indicating greater impairment
- The COMPASS Change Scale is a derivation of COMPASS-select in which the participants score their change in autonomic symptoms since their last exam. It comprises 26 retrospective questions in which participants scored how much their autonomic symptoms had changed. It is divided into change of 6 autonomic function domains (or 5 in women) [i.e. orthostatic intolerance, sexual failure (erectile dysfunction, male only), bladder disorder, secretomotor disorder, constipation and sleep disorder] with a maximum score of 160 for men and 150 for women (Wenning GK et al., 2007).
- MSA-QoL scale is a validated 40 item self-completed questionnaire in which a participant is asked to record the problems due to their MSA over the preceding 4 weeks.
- Timed Motor Tests include a hand tapping task to evaluate the number of hand taps that an individual can perform within 30 seconds and a timed, sit, stand, walk task.
- The Unified Dystonia Rating scale is an objective assessment of the severity of dystonia in each body region.
- Axivity lumbar sensor device. This CE marked sensor will be worn over the lower back (lumbar region), attached using sticky-backed plastic by the research team at the clinic visit, and worn continuously over 1 week prior to the Baseline visit and after the 48 week visit. The sensor will be posted back to the research team at week 49 using a stamp-addressed envelope given out in clinic with clear written instructions and a telephone contact for problems or queries. All recordings will be stored with the unique participant identification number (PIN) as well as their date of birth and gender. Analysis will be performed by [name] team at Newcastle University (sensor data) according to existing analytic protocols.

